#### 9.3. Expected statistical significance

The level of statistical significance is 5%.

#### 9.4. Statistical criteria for discontinuing research

NA

#### 9.5. Missing, unused or invalid data accountability process

The number of missing data and the reason for the missing data will be described for each treatment group.

For patients who do not have an available endpoint at inclusion or at M3, the mean VAS of the randomization group will be imputed in order to analyze the entire randomized population in the intention-to-treat analysis.

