### Study schedule:

Actions	M-1 (Pre-inclusion visit)	M0 (Inclusion visit)	M1	М3	M6	M12
Checking inclusion/non-inclusion criteria	X					
Signing the informed consent		X				
History	X					
Clinical examination		X	X	X	X	X
Randomization		X				
VAS at rest		X	X	X	X	X
VAS for thumb-index grip (during activity)		X	X	X	X	X
VAS for infiltration		X				
Worst Pain Score		X	X	X	X	X
Cochin scale		X	X	X	X	X
Verbal score for overall change			X	X	X	X
Dynamometer (2x3 measurements)		X	X	X	X	X
B-mode and Doppler ultrasound		X		X		
Concomitant treatments (analgesics, NSAIDs)		X	X	X	X	X
Adverse events		X	X	X	X	X

\* Weekly VAS for the first 3 months will be recorded in the patient's diary. The use of new infiltrations, the number of days off work and any progression to a surgical procedure will be recorded during the 12 months of follow-up.

The time allowed for visits at M1 and M3 (primary endpoint) is  $\pm$ 4 days. The time allowed for the other follow-up visits (M6 and M12) is  $\pm$ 4 week.

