# Primary endpoint:

The VAS on activity at 3 months will be compared between groups using a mixed model, taking account of the initial VAS as a fixed effect and the center as a random effect.

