# 9.2. Expected number of participants to be included in the research and expected number of participants in each research location with statistical justification.

The study is a superiority trial that focuses on pain reduction at 3 months. This is assessed on the basis of the difference between the two groups in scores measured between 3 months and baseline. Based on data in the literature, we estimate a mean score of  $6.4 \pm 1.3$  at baseline (Montfort, 2014).

According to the same reference, we assume a 25% reduction in pain in the "corticosteroid alone" group, and a 35% reduction in the "corticosteroid and hyaluronic acid combination" group.

To demonstrate this difference with 80% power and 5% alpha risk, 132 patients will be required.

To ensure sufficient power, 18 additional patients will be included in the study, for a total of 150 patients.

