### 9.7. Choosing the people to include in analyses

The analysis will focus on the Intention-to-treat population.

A sensitivity analysis on the "Per protocol" population will be performed: exclusion of patients with major protocol deviations (non-administration of all products in the randomization arm, new infiltration less than 3 months after the initial infiltration, possible progression to a surgical procedure less than 3 months after the initial infiltration).

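### Filling a missing month-3 activity VAS with the arm's own mean understates the primary standard error: type I error is about 5.6% to 11.7% if 3% to 20% of values are missing, not 5%

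*Combined protocol and SAP*

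**What the plan says.** Section 9.1 makes intention to treat the main analysis. Under its primary endpoint heading it says: "The VAS on activity at 3 months will be compared between groups using a mixed model", with baseline VAS as a fixed effect and centre as a random effect. Section 9.3 sets the significance level at 5%.

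Section 9.5 gives the rule for gaps: "For patients who do not have an available endpoint at inclusion or at M3, the mean VAS of the randomization group will be imputed". Its stated purpose is to keep every randomised patient in the intention-to-treat analysis. It also asks for the number of missing values and the reasons to be described by group.

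The only sensitivity analysis is the per-protocol one in section 9.7, defined by "exclusion of patients with major protocol deviations (non-administration of all products in the randomization arm" and by a new infiltration or surgery within three months. A missing M3 score is not on that list. Section 9 contains no multiple imputation, no variance correction and no observed-case analysis of the intention-to-treat population.

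No expected missing rate is given. Section 9.2 says only: "To ensure sufficient power, 18 additional patients will be included in the study, for a total of 150 patients".

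**The concern.** A patient whose M3 score is missing receives a constant computed from the other patients in the same arm. That constant carries no new information about the treatment effect, yet the model counts it as a full observation lying exactly on the arm mean. The residual variance is therefore too small and the sample size too large, and both errors shrink the standard error.

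This is the primary efficacy test of a superiority trial. When M3 values are missing and there is no true difference, the test rejects more often than the plan says, and the confidence interval is too narrow. The error grows with the number missing, and its size cannot be known when the plan is fixed. Describing the missing data by group shows the extent of the problem but does not correct the test.

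**Working it through.** **Inputs from the protocol.** 150 patients (section 9.2) randomised 1:1 (section 4.3.1), so n = 75 per arm; alpha 5% (section 9.3); baseline VAS 6.4 with SD 1.3, and reductions of 25% and 35% (section 9.2).

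**Assumptions.** M3 values missing completely at random, equally in both arms; no true difference; the value imputed for a missing M3 is the arm's M3 mean (section 9.5 does not name the visit); a two-sided test.

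**The plan's own figure, and sidedness.** The expected difference is 6.4 × (0.35 − 0.25) = 0.64. Two-sided 5%, 80% power: 2 × (1.960 + 0.842)² × 1.3² / 0.64² = 64.8, so 65 per arm. The t-based version gives 65.74, so 66 per arm and 132 in total, which matches "To demonstrate this difference with 80% power and 5% alpha risk, 132 patients will be required". A one-sided 5% test would need 2 × (1.645 + 0.842)² × 1.3² / 0.64² = 51.0, so 52 per arm, or 104. The plan's figure implies a two-sided test.

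**Standard error after filling.** Let k patients per arm be observed, with variance s².
- Correct squared SE of the difference: 2s²/k.
- Filling adds n − k values at the arm mean. The sum of squares stays at (k − 1)s² but is now divided by n − 1, so the reported squared SE is 2s²(k − 1)/[(n − 1)n].
- Reported SE / correct SE = √{[(k − 1)/(n − 1)] × (k/n)}.

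The test rejects when the properly scaled statistic exceeds t_crit × ratio, where t_crit = 1.976 (148 df). Type I error is therefore 2 × P(t with 2k − 2 df > 1.976 × ratio).

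Example, k = 66: ratio = √[(65/74) × (66/75)] = √(0.878 × 0.880) = 0.879; threshold 1.976 × 0.879 = 1.737; with 130 df the two-sided probability is 8.5%.

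| Missing per arm | k | SE ratio | Threshold | Two-sided type I error |
|---|---|---|---|---|
| 2 (2.7%) | 73 | 0.97 | 1.923 | 5.6% |
| 4 (5.3%) | 71 | 0.95 | 1.870 | 6.4% |
| 9 (12%) | 66 | 0.88 | 1.737 | 8.5% |
| 15 (20%) | 60 | 0.80 | 1.578 | 11.7% |

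At 12% missing, coverage of the 95% interval is 100 − 8.5 = 91.5%, and the chance of falsely declaring one given arm superior is 4.2% instead of 2.5%. The 12% row is 18/150. It is the share implied only if the 18 extra patients are meant to cover losses, which section 9.2 does not say.

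**Simulation with baseline adjustment** (SD 1.3; baseline–M3 correlation assumed 0.3 or 0.5; 20,000 runs each; Monte Carlo error about 0.15 to 0.23 points). For 2, 4, 9 and 15 missing per arm: 5.5–5.8%, 6.2–6.6%, 8.5–8.8% and 11.6–11.9%. Observed cases in the same model gave 4.7–5.3%. At 9 missing and correlation 0.5, the mean reported SE was 0.176 against a true SD of 0.201, a ratio of 0.88.

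**Simulation with centre in the model.** Adjusting for baseline and centre gave 5.9%, 6.8%, 8.4% and 11.8%. A REML mixed model with a random centre intercept (three centres, 4,000 runs, error about 0.4 to 0.5 points) gave 8.4–8.5% at 12% missing and 11.2–11.9% at 20%, against 5.4–5.5% with none missing.

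**Baseline gaps.** A missing baseline filled by the same rule gave only 5.1–5.4%. The problem lies with M3.

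**The replacement.** Multiple imputation of M3 by arm from baseline and M1 (20 imputations, 8,000 runs; assumed correlations 0.5 baseline–M1, 0.5 baseline–M3, 0.6 M1–M3) gave 4.8% at 4, 9 and 15 missing per arm. At 9 missing, the reported SE was 0.195 against a true SD of 0.192.

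**The case against.** The strongest objection is that the size rests on a rate the protocol does not give. With complete data there is no inflation, with one missing value per arm it is 5.3%, and 20% missing has no basis in the text. That is fair: the figures are conditional. The direction is not, because any missing M3 value filled this way shrinks the standard error.

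At the low end, the random-centre mixed model cannot separate 5.5–6.0% at 3% missing from its own 5.4–5.5% with none missing. The larger runs and the formula carry that row; the mixed model confirms the inflation at 12% and 20%.

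Two parts of section 9 might be offered as mitigation. The secondary random-effects models of activity pain over M0 to M12 could use incomplete patients without filling. The per-protocol analysis might also use unfilled values, since section 9.5 ties filling to intention to treat. But the first is secondary and the second drops other patients. Neither changes the primary test.

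Two-sided testing and the use of the M3 mean are readings rather than stated facts. The first reproduces the plan's 132, and the second is the natural meaning.

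One related gap stands apart from this point: section 4.2.2.3 calls a new infiltration within three months a treatment failure, but section 9 does not say how that patient's M3 score enters the primary analysis. These passages need reconciling, because the answer decides which values count as missing.

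**Conclusion.** The concern holds. As written, the rule in section 9.5 makes the primary test exceed its 5% level whenever M3 values are missing. The two-sided type I error runs from about 5.6% at 3% missing to 11.7% at 20%, and is 8.5% at 12%. These figures assume 75 per arm, values missing completely at random at equal rates, a two-sided test, and imputation of the arm's M3 mean. They depend little on the baseline–M3 correlation or the centre effect. Nothing is claimed here about bias from informative dropout, and filling a missing baseline is not a material problem for type I error. Because this is the primary analysis, and the error always favours a false positive, it must be fixed.

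**What to change.** Delete the arm-mean rule for M3 and name one replacement as the primary analysis before the data are unblinded.

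- **Likelihood-based model** of the M1 and M3 activity VAS, adjusted for baseline and centre, with the M3 contrast as the primary result. Patients with no post-injection score then contribute no information.
- **Multiple imputation** of M3 by arm from baseline and M1 activity VAS, combined with Rubin's rules. Centre should be in the imputation model, and a missing M1 should be imputed jointly with M3. This keeps all 150 patients, as section 9.5 intends.

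Both use scores already scheduled: the study schedule collects "VAS for thumb-index grip (during activity") at M0, M1 and M3. The weekly diary VAS should serve only as an auxiliary variable, because the protocol does not specify that it measures activity pain. Two optional additions are imputing a missing baseline without using arm, and a delta-adjusted sensitivity analysis for departures from missing at random.

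The cost is analysis-plan wording and some programming. No new data, visits or patients are needed. The confidence interval becomes wider, and correct.

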#### 9.6. Managing changes to the initial strategy analysis plan

NA

### 9.7. Choosing the people to include in analyses

The analysis will focus on the Intention-to-treat population.

A sensitivity analysis on the "Per protocol" population will be performed: exclusion of patients with major protocol deviations (non-administration of all products in the randomization arm, new infiltration less than 3 months after the initial infiltration, possible progression to a surgical procedure less than 3 months after the initial infiltration).

# 10. Right of access to source data and documents

#### 10.1. Data access

In accordance with GCP:

- the sponsor is responsible for obtaining the agreement of all parties involved in the research to guarantee direct access to all research sites, source data, source documents and reports for quality control and audit purposes by the sponsor,

- investigators will make the documents and individual data strictly necessary for controls available to those responsible for monitoring, quality control or auditing biomedical research, in accordance with the legislative and regulatory provisions in force (Articles L.1121-3 and R.5121-13 of the French Public Health Code)

#### 10.2. Source documents

Source documents, defined as any original document or object used to prove the existence or accuracy of data or facts recorded during the clinical study, will be kept for 15 years by the investigator, or by the hospital in the case of hospital medical records.

#### 10.3. Data confidentiality

In accordance with the provisions concerning the confidentiality of data to which those responsible for the quality control of biomedical research have access (article L.1121-3 of the French Public Health Code), and in accordance with the provisions concerning the confidentiality of information relating in particular to the nature of the investigational medicinal products, the trials, the persons involved and the results obtained (article R. 5121-13 of the French Public Health Code), persons with direct access will take all necessary precautions to ensure the confidentiality of information relating to the investigational medicinal products, the trials, the persons involved and in particular their identity, as well as the results obtained.

These people, like the investigators themselves, are bound by professional secrecy (under the conditions defined by articles 226-13 and 226-14 of the French Penal Code).

During or at the end of biomedical research, data collected on subjects and transmitted to the sponsor by the investigators (or any other specialist) will be rendered anonymous.

Under no circumstances may the names or addresses of the persons concerned appear in plain text.

Only the first letter of the subject's last name and the first letter of his or her first name will be recorded, along with a coded number specific to the study, indicating the order of inclusion of subjects.

The sponsor will ensure that each participant in the research has given his or her written consent for access to individual data concerning him or her and strictly necessary for the quality control of the research.

# 11. Quality control and assurance

A Clinical Research Associate (CRA) appointed by the sponsor will ensure that the study is carried out properly, and that the data generated are documented, recorded, and reported in accordance with the Standard Operating Procedures implemented at the CHD Vendée and in compliance with Good Clinical Practice and current legislative and regulatory provisions.

The investigator and members of his team agree to make themselves available for Quality Control visits carried out at regular intervals by the Clinical Research Associate. During these visits, the following elements will be reviewed:

- informed consent
- compliance with the study protocol and procedures defined therein
- quality of data collected in the observation book: accuracy, missing data, consistency of data with "source" documents (medical records, appointment books, original laboratory results, etc.)
- management of any product.

The investigators also agree to quality assurance audits by the sponsor and inspections by the competent authorities. All data, documents and reports may be subject to regulatory audits and inspections, without prejudice to medical confidentiality.

## 12. Ethical considerations

#### 12.1. Ethics committee

The study protocol, information form and consent form will be submitted to the Comité de Protection des Personnes Ile de France III (Ethics Committee) for approval.

Notification of the EC's positive opinion will be sent to the study sponsor and the competent authority.

A request for authorization will be sent by the Sponsor to the ANSM before the start of the study.

# 12.2. Substantial changes

Any substantial modification to the protocol made by the investigator must be approved by the sponsor. Prior to implementation, the sponsor must obtain a favorable opinion from the EC and authorization from the ANSM, within their respective areas of competence. If necessary, a new consent form must be obtained from the participants in the research.

## 12.3. Patient information and the written informed consent form

Patients will be fully and fairly informed, in comprehensible terms, of the objectives and constraints of the study, the possible risks involved, the necessary monitoring and safety measures, and their right to refuse to participate in the study or to withdraw at any time.

All this information appears on an information and consent form given to the patient. The patient's free, informed, and written consent will be obtained by the investigator, or a physician representing him/her, prior to final inclusion in the study. A copy of the information and consent form signed by both parties will be given to the patient, and the investigator will retain the original. At the end of the study, a copy will be placed in a sealed tamper-proof envelope containing all the consent forms, which will be archived by the sponsor.

# 13. Data processing and document and data storage

#### 13.1. Observation notebook

All information required by the protocol must be recorded in the observation notebooks. Data should be collected as they are obtained and recorded explicitly in these notebooks. Any missing data should be coded.

This electronic case report form will be set up in each center, using an Internet data collection medium. Investigators will be provided with a document to help them use this tool.

If the investigator fills in the case report form via the Internet, the CRA can view the data quickly and remotely. The investigator is responsible for the accuracy, quality and relevance of all data entered. What's more, when data is entered, it is immediately checked for consistency. As such, he/she must validate any value modification in the CRF. These modifications are subject to an audit trail. A justification may be included as a comment.

Data will be archived at participating sites.

### 13.2. Data capture and processing

Data will be entered electronically via a web browser.

Data analysis will be carried out by [name], biostatistician, CHD Vendée, La Roche sur Yon.

#### 1.1. CNIL

This study falls within the scope of the "Reference Methodology" (MR-001) relating to data processing, files, and freedoms in application of the provisions of Article 54 Section 5 of the updated Law n°78-17 of January 6, 1978 (Decision 10. 2016-262 of July 21, 2016)

CHD Vendée de La Roche sur Yon, the study sponsor, has signed a commitment to comply with this "Reference Methodology".

#### 13.3. Archiving

At the end of the period of practical use, all documents to be archived, as defined in the standard operating procedures of the CHD Vendée de La Roche sur Yon, will be archived and placed under the responsibility of the Sponsor for 15 years after the end of the study, in accordance with institutional practices.

No removal or destruction may be carried out without the agreement of the Sponsor. At the end of the 15-year period, the Sponsor will be consulted for destruction. All data, documents and reports are subject to audit or inspection.

# 14. Financing and insurance

#### 14.1. Study budget

The study budget was evaluated by the Clinical Research Unit of the CHD Vendée de la Roche sur Yon in agreement with the coordinating investigator.

The budget required to conduct the study was obtained through an internal call for tenders from the CHD Vendée in La Roche sur Yon.

#### 14.2. Insurance

For the duration of the study, the Sponsor will subscribe to a civil liability insurance policy that also covers the physician involved in the study. The Sponsor will also ensure full compensation for any harmful consequences of the research for the participant and his or her beneficiaries, unless it can be proven that the damage is not attributable to the Sponsor or to any other party involved, without being able to invoke the act of a third party or the voluntary withdrawal of the person who had initially agreed to participate in the research.

# 15. Study feasibility

The teams involved in this study include rheumatologists trained in osteoarticular ultrasound, with several years' experience in ultrasound-guided infiltration procedures. Some of these doctors are instructors for a DIU (inter-university diploma) for guided osteoarticular procedures. In terms of recruitment, the CHD Vendée recruits approximately 100 patients with rhizarthrosis requiring infiltration per year, 60 at the CHU Nantes and approximately 40 at the CHG Le Mans, i.e., 200 patients per year (and 300 in 18 months). Taking into consideration non-participants (refusals, non-inclusion criteria, etc.), the number of 150 patients to be included seems realistic.

#### 16. Publication rules

Scientific communications and reports relating to this study will be produced under the responsibility of the principal investigator coordinating the study, with the agreement of the responsible investigators. Co-authors of the report and publications will be the investigators and clinicians involved, in proportion to their contribution to the study, as well as the biostatistician and associated researchers.

Publication rules will follow international recommendations (N Engl J Med, 1997; 336:309-315).

The study will be registered on an open-access website (Clinical trial) prior to the inclusion of the 1st patient in the study.

